6.6.4 Communication with Receiving Ward Staffs

Participants in the study may transfer to another departments after treatment/ care in A&E. The following communication would be conducted:

- A handover note that informs the receiving ward staffs about patients' enrolment to the trial, group assignment, and previous treatments given in A&E. The note would also suggest the investigations for the receiving ward staffs.
- Telephone handover about intervention group and investigations of the study, and treatments given in A&E to ward.

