Objectives	To determine whether the addition of serial CRP levels (with advice on interpretation) to usual care for managing AECOPD leads to a reduction in antibiotic exposure (defined as the total number of antibiotic days by Day 28) for AECOPD without negatively impacting on COPD health status, compared with usual care alone					
Number of Subjects	N=1,184					
Diagnosis and Main Inclusion Criteria	 Being diagnosed with active AECOPD; AND Known COPD in their medical records; AND Age 40 years or older; AND Able to provide informed consent in Cantonese, Mandarin, or English; AND Able to complete the questionnaires during the study period 					
Participation						
Duration	One year					
Interventions	The intervention group will be recommended to test for CRP at randomization and every day during the stay. Antibiotics are considered for discontinuation when CRP reduces below 5mg/dL, on top of existing clinical judgment. The control group will not be tested for CRP and antibiotics will be discontinued according to clinical judgment.					
Main outcome measures and study instruments	The antibiotic exposure (total number of antibiotic days) and recovery in terms of COPD health status (Clinical COPD Questionnaire total scores) within 28 days from randomization. The secondary outcomes include prevalence of potentially pathogenic bacteria and commensal organisms and their proportion of drug-resistant strain, antibiotics prescribed and total antibiotics consumption (doses), adverse effects potentially attributable to antibiotics prescribed for the exacerbation, general health status, disease-specific, health-related quality of life over time measured using the CRQ-SAS (dyspnoea, fatigue, emotion function, mastery and total scores) and costs (total HA cost) and cost-effectiveness.					
Statistical Methodology	 Baseline subject characteristics: descriptive statistics. COPD-related health status, general health status, and duration of antibiotics: Fisher exact tests. Adverse effects and number of events: Chi squared tests. Between-group difference, CCQ score, and EQ-5D: Students' t-test. Group comparison for categorical variables: Fisher 's Exact test All analyses will be performed using Stata software For missing data handling: multiple imputation methods. Cost evaluations: the healthcare provider using standard methods. Cost-effectiveness analysis during the RCT: ITT principle. Health economic outcomes: QALY. 					

4 of 27 31st Oct 2021 1.1

3. Investigators

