A&E is an ideal location to start antibiotic stewardship for AECOPD. Prior work has also been conducted by our team in Hong Kong to ensure the significance of the problem, the feasibility of data collection, and the preliminary results relevant to AECOPD patients with available CRP levels. 21,129 patients were admitted to emergency medicine wards and medical wards through A&E in 2019 (mean age 79 years (IQR 71-86)). Elevated CRP was associated with doubled odds ratio of ICU admission or death (Odds ratio 2.06, 95%CI 1.75 - 2.43). Analysis reveals that 96% of patients with a normal CRP were given antibiotics. Among those with normal CRP, unadjusted statistics suggested those without antibiotics did not have lower odds ratios for deterioration requiring ICU admission and for death (p<0.01) (Appendix 4, Table 1). Overall, AECOPD patients were prescribed antibiotics for a mean of 9.4 days (SD 10.3) but the mean duration of an elevated CRP was 6.4 days (SD 6.8). There is an opportunity to shorten antimicrobial regimen for some AECOPD patients. Further details of the results can be found in Appendix 4, Figure 1 and Figure 2. As personalised antibiotic treatments may reduce healthcare resource utilisation, we sought to determine the optimal antibiotics therapy duration for AECOPD patients based on clinical decision-making and CRP results.

Research Gaps

- 1. Antibiotic stewardship involves both appropriate prescription and timely discontinuation of an antibiotic treatment. Limited evidence informs antibiotic prescription practice for AECOPD in A&E. Information on CRP-guided antibiotic discontinuation is absent.
- 2. Previous studies with hospitalized AECOPD patients with severe symptoms and severe outcomes was insufficient in power.

3. Cost-effectiveness analyses on CRP-guided antibiotic treatment in AECOPD patients are lacking.

5. Aims and Objectives of the study

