6.4 Selection of Subjects

6.4.1 The inclusion criterion:

The inclusion criteria are ALL of the below:

- Being diagnosed with active AECOPD (AECOPD is defined as an event in the natural course of a disease characterized by a change in baseline dyspnoea, cough, and/or sputum that is beyond the normal day-to-day variations with acute onset, which may warrant a change in regular medication in patients with underlying COPD).⁵
- 2. Known COPD in their medical records.
- 3. Age 40 years or older.
- 4. Able to provide informed consent in Cantonese, Mandarin, or English
- 5. Able to complete the questionnaires during the study period (i.e. 6 months after randomisation)

6.4.2 The exclusion criteria:

Patients will be excluded if any ONE of the following are present:

1. Pre-treatment with systemic corticosteroids for the present exacerbation.

- 2. Pre-treatment with any antibiotics for the present exacerbation, any concurrent infection or prophylaxis.
- 3. Known clinical stroke in past 6 months
- 4. Patients with high suspicion of active AECOPD mimics:
 - 1) Pneumonia
 - 2) Congestive heart failure
 - 3) Bronchiectasis
 - 4) Pulmonary embolism
 - 5) Pneumothorax
 - 6) Atrial fibrillation / flutter
- 5. Lung comorbidities:
 - 1) Cystic fibrosis
 - 2) Tuberculosis
 - 3) Unresolved lung malignancy
- 6. Progression or new radiographic abnormalities on the chest X-ray.
- 7. Immunodeficiency disorders such as AIDS, humoral immune defect, ciliary dysfunction etc., and the use of immunosuppressive drugs for more than 28 days.
- 8. Active inflammatory condition (e.g. flare up of rheumatoid arthritis, gout or polymyalgia rheumatica) or concurrent infection at another site (e.g. UTI, cellulitis) that is likely to produce a systemic response
- 9. Currently pregnant
- 10. NEWS2 score¹⁹ of \geq 3

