6.5 Intervention

This is a two-arm, open, single-blind, single-centred, individually randomised controlled trial involving emergency physicians in ED. This trial will evaluate the addition of serial CRP levels to usual care to guide antibiotics management decisions for patients presenting in ED with AECOPD, which is the first in the world. Patients presenting with AECOPD will be randomised to clinical management based on usual care alone or usual care with the addition of a serial CRP levels.

Control arm

Patients in the control arm will be treated with usual care (GOLD initiative). No CRP would be measured.

Intervention arm

Training in CRP interpretation will help to guide decisions about the use of antibiotic treatment for AECOPD. All serum CRP tests will be conducted by the local pathology laboratory in each

participating hospital. These laboratories have been accredited by Hong Kong Laboratory Accreditation Scheme (HOKLAS) based on ISO standards.

The attending doctor will use the CRP level to inform their decision to continue antibiotics around 3 hours from blood taking. These doctors will be provided pre-study training on CRP interpretation.

Every day from randomization, serum CRP testing will be encouraged to take. Once CRP has declined to <5mg/dL and the patient has remained afebrile for past 48 hours, antibiotic treatment will be reviewed for discontinuation. Otherwise, antibiotic treatment will be continued. A switch on the administration route, or a change of antibiotics due to adverse effect, allergy, or suggestion from culture result, is permitted according to in-patient physician's decisions. CRP will continue to be monitored daily upon discharge from that hospital (up to 28 days).

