6.6.2 Randomization

Patients will be randomized at ED (Day 1). They are randomised in a 1:1 ratio to receive either usual care alone (control), or usual care with addition of CRP trend monitoring for discontinuation of antibiotics. The randomization sequence will be centralised. Computergenerated and randomly permuted blocks allocations will be used. Exacerbation classification suggested by GOLD Initiative is adopted as a minimisation variable so that balance is achieved with respect to differing levels of COPD exacerbation severity.

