Trained physicians and nurses will help with patient recruitment and data collection in the busy emergency departments.

Baseline subject characteristics will be reported using descriptive statistics such as percentage, medians, and interquartile ranges. COPD-related health status, general health status, and duration of antibiotics use will be compared among groups by Fisher exact tests. Adverse effects and number of events in the intervention group compared to control group will be noted and compared by Chi squared tests.

To estimate the between-group difference on primary outcome of antibiotic duration, two sample T test will be used to the analysis. The other continuous variables including the co-primary outcome (CCQ score) and secondary outcome (EQ-5D) will be analyzed in the same manner.

Fisher 's Exact test will be used to make group comparison for categorical variables such as COPD Severity (GOLD grading), COPD exacerbation severity (Anthonisen criteria) and microbiological pathogen. All available data will be summarized descriptively by tables and figures. All analyses will be performed using Stata software (version 16 or updated version) and considered significant at p<0.05.

For missing data handling, multiple imputation methods will be used to assess the sensitivity of primary outcome results to missing data. Assuming at random, generalised linear models will used for the multiple imputations.

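### Patients sent home from the ED may get only the first CRP, diluting both co-primary comparisons; intended disposition should be recorded before allocation

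*Combined protocol and SAP*

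**What the plan says.** **Who is randomised.** Section 6.3 has patients screened on arrival in A&E, and Section 6.6.2 places randomisation in the ED on Day 1. Section 6.4.1 opens with "The inclusion criteria are ALL of the below" and lists five criteria; admission is not among them. Section 6.4.2 excludes NEWS2 of 3 or more. Section 6.6.4 says "Participants in the study may transfer to another departments after treatment/ care in A&E", which allows a move to a ward but does not require one.

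**What the intervention is.** The Study Summary (Section 2) says "The intervention group will be recommended to test for CRP at randomization and every day during the stay". Section 6.5 encourages testing daily from randomisation, in the hospital's own laboratory. Antibiotics are reviewed for stopping once CRP has fallen below the threshold and "the patient has remained afebrile for past 48 hours"; changes of route or drug are left to the in-patient physician. Its last sentence has CRP monitored daily upon discharge, for up to 28 days. Section 6.6.2 describes the randomised difference as CRP trend monitoring for discontinuation.

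**Follow-up.** Section 6.6.8 describes remote weekly contact, a week-4 clinical follow-up and one return for samples before the end of week 5. It gives no procedure for drawing blood or reviewing antibiotics at home before then.

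**Planning data and analysis.** The background (Work done by us) reports that "21,129 patients were admitted to emergency medicine wards and medical wards through A&E in 2019", with mean antibiotic duration 9.4 days (SD 10.3) and mean duration of elevated CRP 6.4 days. Section 9 states: "To estimate the between-group difference on primary outcome of antibiotic duration, two sample T test will be used to the analysis". CCQ is analysed in the same manner. Section 9 names the ITT principle only for cost-effectiveness.

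**The concern.** The discontinuation part of the strategy needs repeated CRP results, 48 hours of observation for fever, and a doctor who acts on them. All three are described for patients in hospital. A patient sent home on Day 1 has the ED result and, as the text stands, no described route to the rest. Excluding higher NEWS2 scores leaves lower-acuity patients, who may reasonably be thought more likely to go home, although the protocol gives no figure.

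Patients whose care differs by one CRP result pull the arms together on both co-primary outcomes. For antibiotic days this costs power. For CCQ it works in the trial's favour, because a diluted difference is easier to place inside a non-inferiority margin. The trial could then report that serial-CRP-guided discontinuation is safe when part of the sample never had it. Because treating physicians are unblinded (Section 6.6.3), allocation could influence actual admission, so a later subgroup by actual admission would be open to bias.

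**Working it through.** **The stated sample size.** N = 1,184 gives 1,184/2 = 592 per arm. The available text gives no effect size, power, CCQ margin, CCQ SD or dropout rate, so the figure cannot be reproduced. The planning data contain a gap of 9.4 − 6.4 = 3.0 days. With SD 10.3 and two-sided 0.05, that gap needs 372 patients in total for 80% power, 496 for 90% and 614 for 95%, none of which is 1,184.

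**Inputs for the dilution check**
- From the protocol: 592 per arm; SD 10.3; two-sample t-test; significance at p<0.05, taken as two-sided because the sidedness is not stated; the 3.0-day gap.
- Assumed: the share f discharged from the ED (range shown); an alternative effect of 2 days; no effect at all in discharged patients, which is the worst case; the same SD in discharged patients; no loss to follow-up.

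**Antibiotic days**

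SE = 10.3 × √(2/592) = 0.599

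All-randomised difference = d × (1 − f); power = Φ(d(1 − f)/0.599 − 1.96)

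| f | Assumed 2-day effect: difference, power | 3.0-day gap: difference, power |
|---|---|---|
| 0% | 2.0, 91.6% | 3.0, 99.9% |
| 20% | 1.6, 76.2% | 2.4, 98.0% |
| 30% | 1.4, 64.7% | 2.1, 93.9% |
| 40% | 1.2, 51.8% | 1.8, 85.2% |
| 50% | 1.0, 38.6% | 1.5, 70.7% |

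The difference detectable with 80% power is 1.68 days. Power therefore falls below 80% once f exceeds 1 − 1.68/2 = 16% for a 2-day effect, or 1 − 1.68/3 = 44% for the 3.0-day gap.

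**CCQ non-inferiority.** The margin and SD are not in the available text. As an illustration, assume margin 0.3, SD 1.2 and one-sided 0.025, and suppose admitted patients are worse by exactly the margin while discharged patients are unaffected.

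SE = 1.2 × √(2/592) = 0.0697; chance of declaring non-inferiority = Φ(0.3f/0.0697 − 1.96)

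This gives 2.5% at f = 0, 6.3% at 10%, 13.6% at 20%, 25.2% at 30% and 57.6% at 50%. At f = 30% the result runs from 10% to 54% over margins 0.2 to 0.4 and SDs 1.0 to 1.5.

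**The case against.** A reader might infer that discharged patients cannot receive serial CRP. The protocol does not support that. Section 6.5 encourages testing every day from randomisation, and its last sentence can mean monitoring after discharge as well as until discharge. What stands is narrower: that sentence and the Study Summary do not agree on testing outside the stay, and no means of delivering it is described.

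Zero effect in discharged patients is also an extreme. Hypothesis (i) in Section 5.2 covers prescription as well as discontinuation. The background cites a primary-care trial in which CRP testing went with antibiotic use of 57.0% against 77.4%, and a hospital trial with 31.7% against 46.2% where stopping was left to clinical judgment in both arms. It also reports that 96% of patients with a normal CRP were given antibiotics. The first CRP alone could therefore shift antibiotic days, and not prescribing in the ED could affect CCQ. This makes the figures above upper bounds on dilution. It also means the pooled result would mix two mechanisms that the plan has no way to separate.

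Not transferring is not the same as going home: the planning data include emergency medicine wards, and Section 6.2 also allows recruitment through medical wards. The participant flow diagram (Appendix 6) is not visible, so a disposition step there cannot be ruled out.

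Finally, Section 5.1 asks about AECOPD patients in Emergency Departments. Including discharged patients is a legitimate choice of population, and the all-randomised comparison answers that question. The protocol gives no ground for calling the missing admission criterion an error.

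**Conclusion.** The concern holds in a limited form. Patients may be discharged from the ED after randomisation, the protocol is inconsistent on whether serial CRP follows them, and nothing in the analysis distinguishes them. Any resulting dilution works against superiority on antibiotic days and towards non-inferiority on CCQ.

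Its size cannot be fixed from the documents. It would be tempting to conclude that the trial is underpowered, but that depends on an assumed 2-day effect and an assumed discharge share. On the protocol's own 3.0-day gap, power stays above 80% until a little over 40% of patients are discharged without effect. That gap is itself a difference between two means in admitted patients, not a stated planning effect.

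The CCQ side deserves more weight, because the chance of a false non-inferiority claim about serial monitoring rises even at a low discharge share. Those percentages rest on an assumed margin and SD and on no CCQ effect in discharged patients. This is a cheap improvement to the plan, not a flaw that invalidates it.

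**What to change.** 1. Reconcile the Study Summary with Section 6.5 on CRP testing outside the hospital stay, and describe how whatever is intended will be delivered and acted on.
2. In Sections 6.6.1 to 6.6.3, have the attending physician record the intended disposition (admit or discharge) before the envelope is opened.
3. In Section 9, adjust both co-primary analyses for intended disposition, which means a linear model with arm and disposition in place of the plain two-sample t-test.
4. Pre-specify, as a supportive analysis, both co-primary effects among patients with a recorded decision to admit, reported beside the all-randomised result. Do not attribute CCQ non-inferiority to serial-CRP-guided discontinuation without showing it.

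This does not call for an admission criterion, nor for non-inferiority to be met formally in both sets. Either would trade recruitment or power for a narrower question, and that is the sponsor's choice.

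The cost is one form item, some analysis wording and a less precise supportive estimate. If half are discharged, the supportive set has 296 per arm: SE = 10.3 × √(2/296) = 0.847, and power for a 2-day effect is Φ(2/0.847 − 1.96) = about 66%. The step must be in place before recruitment, because intended disposition cannot be recovered without bias once the allocation is known.

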6.6.5 Data collection

Trained physicians and nurses may help patient recruitment and data collection in busy emergency departments.

6.6.6 Procedure

The attending emergency physician who sees the patient will report the duration of AECOPD symptoms, medication history, and physical findings (temperature, pulse, oxygen saturation, respiratory rate, abnormal lung sounds and peak expiratory flow rate before and after bronchodilators). The patient was treated according to GOLD initiative, including bronchodilator, and systemic steroid. A sputum sample, a throat swab sample (for bacterial culture) and a nasopharyngeal swab (for respiratory virus – pneumonia panel) are collected. The attending physician will assess and record the sputum colour using the Bronkotest chart (Appendix 8). That patient will be interviewed for CCQ an EQ-5D-5L questionnaire.

Patients randomised to the intervention group will be recommended to have CRP tested and the result will be recorded in the proforma. Medication (including antibiotics) prescription and other management plan will be recorded.

Trial team members will collect healthcare service utilization data, spirometry result, laboratory results and antibiotics prescribed for 12 months before randomization.

6.6.7 Microbiological assessment

Sputum, throat swab and nasopharyngeal swab samples, which are obtained in the initial encounter and in week-4 follow up, are sent to local hospital laboratories. Sputum sample is not necessarily available, depending on the symptomatology.

All samples will be prepared and tested according to hospital standard operation procedure. Bacteria found in the sputum sample will be identified using the Matrix Assisted Laser Desorption Ionising Time of Flight Mass Spectrometry (MALDI-ToF-MS) and semi-quantitative counts recorded. The throat swab for bacterial culture & sensitivity should be collected using sterile swabs and placed into Amies transport medium (+/- charcoal). A sheep blood agar plate (BA) is inoculated and incubated at 35 - 37 °C for 20 - 24h in 5 – 10% CO₂. Nasopharyngeal swab sample is collected with flexible wire shaft swab and transported in viral transport media. The sample will be tested for RT-PCR for respiratory viruses.

6.6.8 Follow Up

The trial team will aim to contact all participants through telephone call, or audio / video call with instant messaging software and application service such as WhatsApp, WeChat, or Instant Messenger, every week after randomization to follow up CCQ and EQ-5D questionnaires. The patient will be met on video call at 4-weeks post randomization. A copy of Chronic Respiratory Disease Questionnaire, self-administered, standardized (CRQ-SAS) and EQ-5D will be sent to patients for completion and return at 6 months.

Week 1 & Week 3

Follow-up call for *week 1 and 3* (±1 working day): The patient will be interviewed for the symptomatology, CCQ and EQ-5D questionnaires.

Week 4

Clinical follow up at *week 4* (±2 working days) by research clinician for medication consumption, adverse effects, sick leave, diagnosis of pneumonia since the initial encounter, any further CRP tests since the initial encounter, health care consultations, CCQ and EQ-5D. The patient will be required to return to the emergency department to undergo fresh sputum collection, throat swab and nasopharyngeal swab anytime during the day of weekdays before end of week 5. The colour of the sputum specimen will be examined. If the patient defaults the follow up at week 4, the team will contact the patient again and collect as many data items as possible. If the patient is unable to present, follow up call will be performed.

Month 6

At *6-months* post randomisation, the trial team member will examine the patient's medical record for any spirometry results, prescription, and healthcare service utilization. The patient will also be sent a copy of CRQ-SAS and EQ-5D then for self-completion. A text reminder message will be sent through with instant messaging software and application service application. Defaulted patients will be called for interview to collect their responses.

7. Assessment of Efficacy

Mean antibiotic duration (in days) within 28-days for AECOPD after randomization.

8. Assessment of Safety

Adverse Event

Events fulfilling the definition of a serious adverse event (SAE), including death, emergency hospitalization for conditions other than AECOPD, life-threatening medical conditions, (required preventive intervention for) disability or permanent damage, or other serious medical events that occur between randomization and 4-week post randomization will be reported to the trial team as soon as it is detected.

9. Statistics and Data Analysis

Trained physicians and nurses will help with patient recruitment and data collection in the busy emergency departments.

Baseline subject characteristics will be reported using descriptive statistics such as percentage, medians, and interquartile ranges. COPD-related health status, general health status, and duration of antibiotics use will be compared among groups by Fisher exact tests. Adverse effects and number of events in the intervention group compared to control group will be noted and compared by Chi squared tests.

To estimate the between-group difference on primary outcome of antibiotic duration, two sample T test will be used to the analysis. The other continuous variables including the co-primary outcome (CCQ score) and secondary outcome (EQ-5D) will be analyzed in the same manner.

Fisher 's Exact test will be used to make group comparison for categorical variables such as COPD Severity (GOLD grading), COPD exacerbation severity (Anthonisen criteria) and microbiological pathogen. All available data will be summarized descriptively by tables and figures. All analyses will be performed using Stata software (version 16 or updated version) and considered significant at p<0.05.

For missing data handling, multiple imputation methods will be used to assess the sensitivity of primary outcome results to missing data. Assuming at random, generalised linear models will used for the multiple imputations.

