Secondary outcome measures include adverse effects potentially attributable to antibiotics prescribed for the exacerbation, general health status measured by EuroQoI-5D (EQ-5D),

Costs (total HA cost) and cost-effectiveness, Disease-specific, health-related quality of life over time measured using the CRQ-SAS (dyspnoea, fatigue, emotion function, mastery and total scores).

11. Direct Access to Source Data/ Documents

The investigators and the research assistants in the research team will be responsible for data collection of the project. The investigators will permit trial-related monitoring, audits, IRB review, and regulatory inspection(s), providing direct access to source data and documents.

12. Ethics

The trial will be conducted in accordance with the principles originating in the Declaration of Helsinki, and those in Good Clinical Practice. After patients (or relatives/legal representatives) are assessed as suitable for the Trial, all subjects for this study will be provided a consent form describing this study and providing sufficient information for subjects to make an informed decision about their participation in this study. This consent form is submitted with the protocol for review and approval by the Institutional Review Board (IRB) for the study. The formal consent of a subject, using the IRB-approved consent form, must be obtained before that subject is submitted to any study procedure. This consent form must be signed by the subject or legally acceptable surrogate, and the investigator-designated research professional obtaining the consent. The trial will be conducted in accordance with the information and consent forms.

13. Data Handling and Record Keeping

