Primary	To determine whether the addition of a serial CRP levels (with advice on interpretation) to usual care for managing AECOPD leads to a reduction in antibiotic exposure for AECOPD without negatively impacting on COPD health status compared to usual care alone.	Recovery in terms of COPD health status as assessed using the Clinical COPD Questionnaire (CCQ) total scores	2 week
Secondary	To evaluate the effect of serial CRP levels for AECOPD in emergency department on:	Prevalence of potentially pathogenic bacteria cultured from sputum at 4 weeks and the proportion of bacteria that are resistant	4-week
		Prevalence of commensal organisms cultured from sputum at 4 weeks and the proportion of bacteria that are resistant	4-week
		Adverse effects potentially attributable to antibiotics prescribed for the exacerbation	Weekly for 4 weeks
		All-cause antibiotic consumption	During the first 4 weeks post randomisation
			week
		orally administered steroids	4-week
		General health status measured by EuroQol-5D (EQ-5D)	Weekly for 4 weeks
		Primary and secondary care consultations, including hospitalisations	4-week & 6-month
		Costs (total HA cost) and cost-	6 month
		Incidence of pneumonia (measured by patient and medical record)	4-week & 6-momnth
		Disease-specific, health-related quality of life over time measured using the CRQ- SAS (dyspnoea, fatigue, emotion function, mastery and total scores)	6-month

Key: AECOPD acute exacerbation of chronic obstructive pulmonary disease, CCQ Clinical COPD Questionnaire, CRP C-reactive protein point-of-care test, CRQ-SAS Chronic Respiratory Disease Questionnaire, self-administered, standardised

Participant Flow Diagram

CONSORT 2010 Flow Diagram

BRONKOTEST

ERS

Evaluation of sputum colour

Sputum purulence correlates with presence of bacteria and favourable effect of antibiotics

european respiratory society every breath counts

Source: https://www.ersnet.org

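### The SAE hospitalisation criterion exempts every emergency admission for AECOPD, not only the index one, and AECOPD readmission is not a named safety outcome elsewhere

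*Combined protocol and SAP*

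**What the plan says.** Section 8 (Assessment of Safety) lists the events that count as serious. The hospitalisation element reads "emergency hospitalization for conditions other than AECOPD". The list also contains death, life-threatening conditions and "disability or permanent damage, or other serious medical events", none of which carves out AECOPD. Events "that occur between randomization and 4-week post randomization will be reported to the trial team as soon as it is detected".

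Section 9 gives one sentence on the comparison of harms: "Adverse effects and number of events in the intervention group compared to control group will be noted and compared by Chi squared tests". It does not define which events are meant.

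The safety-type secondary outcome in Section 10 is "adverse effects potentially attributable to antibiotics prescribed for the exacerbation". Appendix 5 repeats it and adds, as secondary outcomes at 4 weeks and 6 months, "Primary and secondary care consultations, including hospitalisations" and the incidence of pneumonia.

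Section 6.6.8 has the week-4 follow-up ask about "any further CRP tests since the initial encounter, health care consultations, CCQ and EQ-5D". Review of the medical record for service utilisation is specified at 6 months.

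**The concern.** The intervention uses serial CRP to prompt review of antibiotics for discontinuation, and Section 5.2 aims to show that this can be done safely. If antibiotics were stopped too early, one plausible consequence is relapse of the treated condition and a further emergency admission for it. That is the one kind of emergency admission the SAE criterion leaves out.

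The exemption has an evident reason. Patients enter the trial with AECOPD and many will be admitted for it, so reporting the index admission as an SAE would be pointless. The wording goes further, though, and also removes any later admission for AECOPD.

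The named safety-type outcome in Section 10 concerns harm from antibiotics that were given, which shorter treatment should reduce if it changes it at all. As written, the safety plan is better placed to register the benefit of stopping early than its possible cost.

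**Working it through.** No figure in the plan needs reproducing. The check sets the text side by side and then adds an illustration of scale.

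**Where would an AECOPD readmission be picked up?** Take a patient who is discharged, then readmitted as an emergency for AECOPD on day 20, and whose life is not in danger.

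| Route | Is it captured? |
|---|---|
| Section 8, hospitalisation element | No; exempt by cause |
| Section 8, death or life-threatening | No; not met |
| Section 8, catch-all for other serious events | Unclear; a site that reads the explicit exemption is unlikely to report it here |
| Section 9, chi-squared test on number of events | Unclear; events are not defined |
| Section 10, secondary outcomes | No; hospitalisation is not listed |
| Appendix 5, consultations including hospitalisations | Yes, but pooled with primary care contacts and all causes, with index and later admissions not separated |
| Co-primary CCQ at day 14 | No; the questionnaire asks about the past week (Appendix 1), so it covers roughly days 8 to 14 |

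On timing, the background text reports a time to next exacerbation of 32 and 28 days in the two arms of the cited trial in hospitalised patients. Many relapses could therefore fall after the day-14 assessment. CCQ is also collected at later weekly contacts, but Section 10 and Appendix 5 set the co-primary outcome at 14 days. SAE reporting is the only prompt route described; Appendix 5 evaluates hospitalisations at week 4 and month 6.

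**Scale (illustration only).** Inputs:
- N = 1,184 (Study Summary), 1:1 allocation (Section 6.6.2), so n = 1,184 / 2 = 592 per arm with no allowance for loss.
- 28-day AECOPD readmission proportion p: not in the documents; assumed 5% to 30%.

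Formulae:
- Expected patients with an event per arm = 592 × p.
- 95% CI half-width on the risk difference, equal proportions = 1.96 × √(2p(1−p)/592). At p = 0.05: 1.96 × √(0.095/592) = 0.025. At p = 0.30: 1.96 × √(0.42/592) = 0.052.
- Power for a 1.5-fold rise, two-sided 5% level, normal approximation with pooled variance under the null. At 10% against 15%: (0.05 − 1.96 × 0.01922)/0.01917 = 0.64, giving power of about 74%.

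| Assumed p, control | Patients with an event, control arm | 95% CI half-width (points) | Power for 1.5-fold rise |
|---|---|---|---|
| 5% | 30 | 2.5 | 43% |
| 10% | 59 | 3.4 | 74% |
| 15% | 89 | 4.1 | 91% |
| 20% | 118 | 4.6 | 98% |
| 30% | 178 | 5.2 | >99% |

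At the planned size, then, a named comparison would be informative over most of this range, though not at the lowest rates.

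**The case against.** The strongest reply is that the harm is measured, only not under the SAE label. Appendix 5 lists hospitalisations and pneumonia as secondary outcomes at two time points, in rows separate from costs. A research clinician asks about consultations at week 4, and utilisation is taken from the record at 6 months. A fatal or life-threatening exacerbation is an SAE whatever its cause. The claim of no detriment rests on CCQ, which Section 10 justifies as showing delayed recovery, and not on SAE counts.

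All of that stands. It rules out several stronger readings that a reader might be tempted to make:

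- *That AECOPD relapse goes uncounted.* The documents do not support this: it is counted within all-cause hospitalisation. What is missing is the split by cause, the separation from the index admission and a stated analysis.
- *That the event is known to be common.* The background text quotes 30-day treatment failure of 44.5% against 45.5% from the cited hospital trial. Treatment failure is not defined there and is not a readmission rate. This trial also excludes patients with NEWS2 of 3 or more, so a rate from hospitalised patients may not carry over.
- *That relapse is the most likely harm.* This is a reasonable inference from the intervention, but no passage ranks the harms.
- *That every emergency department re-attendance for AECOPD should be an SAE.* Attendance without admission does not meet Section 8's own hospitalisation criterion.

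What the reply does not answer is that a pooled item without cause cannot show whether an excess lies in AECOPD admissions, and that the explicit exemption tells sites not to report such an admission promptly.

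**Conclusion.** The concern holds in a limited form. A non-fatal, non-life-threatening emergency readmission for AECOPD within 4 weeks is exempt from the SAE hospitalisation criterion, because the exemption covers all AECOPD admissions and not just the first. It would be counted only in an undifferentiated Appendix 5 outcome that Section 10 omits and Section 9 does not analyse on its own. CCQ at day 14 covers part of the gap.

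The effect is on the trial's ability to support its safety aim, not on either co-primary analysis. Its size cannot be read from the documents. On assumed 28-day rates of 5% to 30% and 592 patients per arm with complete follow-up, about 30 to 178 patients per arm would have such an event, and the difference between arms could be estimated to within about 2.5 to 5.2 percentage points.

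**What to change.** In Section 8, limit the exemption to the index admission, so that a later emergency admission for AECOPD between randomisation and 4 weeks is reported as an SAE.

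At minimum, whether or not the SAE wording changes, name emergency readmission for AECOPD after the index episode as a safety outcome in Sections 9 and 10 and Appendix 5:

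- Define the end of the index episode (for example first discharge home from the emergency department or ward, with transfers during that stay not counted).
- Count patients with at least one event, out of all randomised, by allocated arm.
- Have the cause of each admission coded by an assessor blinded to arm, which fits Section 6.6.3.
- Report the risk difference with 95% CI at 4 weeks, from questions at the week-4 follow-up, and at 6 months, from the utilisation record review already planned. Show deaths alongside.
- State which events the chi-squared comparison in Section 9 covers.

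The cost is coding the cause of admissions and, if the SAE wording is changed, some additional SAE forms. No new visit is needed. The week-4 figure will rest mainly on patient report unless a record check is added then, since utilisation from the record is specified only at 6 months.
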